14.3 Analysis of the primary endpoint

Correct placement of the stent into the ureter as visualised on KUB plain x-ray post procedure.

14.4 Analysis of the secondary endpoints

- The mechanical reliability of the JSI to perform its function as expected.
- The clinical safety of the JSI
- Time taken to insert the ureteric stent using JSI
- Feasibility- evaluation of participant recruitment rate
- Participant experience and satisfaction with the JSI
- User satisfaction for urological doctor/study researcher.
- Engagement and acceptability to surgical, medical and nursing hospital staff

- Impact on workflow data
- Impact on health economics

14.5 Analysis Populations

Analysis of the primary objective will be conducted using the intent-to-treat sample including all participants treated with the JSI.

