8.3 STUDY OUTCOME MEASURES

8.3.1 Primary endpoint:

- The ability of the JSI to correctly insert a stent into the ureter of a suitable participant as determined by post-stenting KUB plain X-ray.
 - Timepoint: Immediately post-stent insertion with KUB Xray
 - Measure: Investigator's assessment of position of superior part of stent within kidney collecting system on KUB plain X-ray performed after stent insertion (Yes/No/Unsure)
 - If "Unsure"- proceed to renal ultrasound to confirm.
 - If "No" or still "Unsure" then proceed to standard stent insertion in operating room

8.3.2 Secondary endpoints:

- The mechanical reliability of the JSI to perform its function correctly as determined by the treating doctor as noted on a global doctor satisfaction score.
 - Timepoint: Immediately post-device usage
 - Measure: Rating of device reliability, i.e. correct mechanical function to work as intended on global doctor satisfaction score.
- The clinical safety of the JSI.
 - Timepoint: Immediately post-intervention commencement through to final follow up visit.
 - Measure: Assessed using reported adverse events, device deficiencies and participant questionnaire.
- Time taken to insert the ureteric stent using JSI (measures stent insertion procedure time only, workflow data assesses overall workflow and will be assessed separately).
 - Timepoint: Immediately post-intervention commencement.
 - Measure: Use of stopwatch or calculated from start and end times and recorded on a

case report form.

- Feasibility- evaluation of participant recruitment rate.
 - Timepoint- At study completion. To be completed within 6 months of study commencement.
 - Measure: A log will be kept of all participants invited to the study and if applicable, their reasons for refusal noted. Feasibility will be assessed using recruitment/withdrawal data and an audit of study enrolment and withdrawal logs.
- Participant experience and satisfaction with the JSI.
 - Timepoint: Prior to stent insertion (within 2 hours), Post stent insertion (within 1 hour), and at follow up visit for definitive stone management surgery (within 14-21 days)
 - Measure: Participants will receive a Patient Satisfaction Questionnaire regarding their experience of ureteric stent insertion with the JiffyStent Inserter.
- User satisfaction for urological doctor/study researcher.
 - Timepoint- Immediately after stent-insertion.

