9.2 Schedule of Assessment

| Assessments | Screening (Day -7 to Day 1) | Procedure (Day 1) | Follow Up Visit (14 to 21 Days Post Tx) |
|------------------------------|--------------------------------|----------------------|--|
| Informed consent | X | | |
| Inclusion/Exclusion Criteria | X | | |
| Medical History | X | | |
| Demographics | X | | |
| CT Scan / MRI | X ^a | | |
| KUB X-Ray | | X ^b | |
| Renal Ultrasound | | (X) ^c | |
| User Questionnaire | | X ^d | |
| Participant Questionnaire | | X ^e | X |
| Device Deficiencies | | X | |
| Adverse Events | X | X | X |
| Concomitant Medications | X | X | X |
| Stone Management | | | X ^f |

- a. Prior imaging may be collected up to 30 days prior to treatment
- b. Performed after stent insertion for confirmation of position of the stent.
- c. If unable to confirm stent positioning via X-Ray, then proceed to perform renal ultrasound
- d. Performed ‘Immediately after stent-insertion’
- e. Performed ‘Prior Insertion’ and ‘Post Insertion’
- f. As per standard practice

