9.7 Definition of enrolment

Time at which, following recruitment and before any clinical investigation-related procedures are undertaken, a participant who meets the eligibility criteria signs and dates the informed consent form.

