11.2.3 Device Electrical Risks

| Hazard | Risk | Mitigation and residual risk |
|--|---|--|
| 
Smart device will not connect with JiffyStent Inserter Wi-Fi
 
Probability: Possible Severity: negligible
 | 
Procedure cannot be commenced. No harm to participant.
 | 
Quality design and manufacture principles of board and WIFI components. Extensive mechanical, electrical and aging/transport testing. participant goes to theatre for standard procedure. Careful instructions on smart devices that can be used with device.
 |

| | | |
|---|--|---|
| 
Smart device disconnects from JiffyStent Inserter Wi-Fi
 
Probability: Possible Severity: negligible
 | 
Procedure cannot be completed. Minimal harm to participant. Financial risk with single use device.
 | 
Quality design and manufacture principles of board and WIFI components. Extensive mechanical, electrical and aging/transport testing. Device can be removed without injury to participant. If stent is partially deployed, it can be removed or if in urethra then the only downside is temporary incontinence. Participant taken to theatre for stent removal and insertion of new stent.
 |
| 
Battery runs out on JiffyStent Inserter
 
Probability: Possible Severity: negligible
 | 
Loss of vision on smart device screen. No harm to patient. Financial risk with single use device.
 | 
Device can be removed without injury to patient. If stent is partially deployed, it can be removed or if in urethra then the only downside is temporary incontinence. Patient taken to theatre for stent removal and insertion of new stent. Battery will have a minimum 30 min run time. This would be considered well beyond a reasonable time to successfully complete a stent insertion outside of the operating room.
 |
| 
Smart device runs out of battery during procedure
 
Probability: Possible Severity: minor
 | 
loss of vision on smart device screen. No harm to participant. Financial risk with single use device.
 | 
Educational material and online course could state the importance of having adequate battery life before commencing procedure. Replace battery or replace device or take to operating room as per standard procedure.
 |

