14.8 Missing Data

Every effort will be made to collect all data points in the study. The Sponsor plans to minimise the amount of missing data by appropriate management of the prospective clinical study, proper screening of study participants, and training of participating investigators, monitors and study coordinators. All partial data that is available on participants who drop out during the course of the study will be included. No imputation will be performed for study outcomes.

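### The primary analysis set and scoring rules let failed JSI attempts leave the denominator or go unscored, so the placement success rate can be overstated

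*Protocol*

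**What the plan says.** Section 14.5 of the protocol reads: "Analysis of the primary objective will be conducted using the intent-to-treat sample including all participants treated with the JSI". The protocol does not say whether treated means package opened, device inserted or stent deployed, and the synopsis gives the analysis sets as not applicable. Section 9.7 places enrolment earlier, at the time when "a participant who meets the eligibility criteria signs and dates the informed consent form".

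The endpoint measure in section 8.3.1 is the investigator's "assessment of position of superior part of stent within kidney collecting system on KUB plain X-ray performed after stent insertion (Yes/No/Unsure"; an Unsure reading goes to renal ultrasound. A No, or a reading still Unsure after ultrasound, sends the participant for standard stenting in theatre. The schedule in section 9.2 times the KUB X-ray the same way: "Performed after stent insertion for confirmation of position of the stent".

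Section 14.3, on the primary analysis, says only: "Correct placement of the stent into the ureter as visualised on KUB plain x-ray post procedure". Section 14.8 adds: "No imputation will be performed for study outcomes".

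The protocol also foresees attempts that yield no JSI stent. If the smart device will not connect, section 11.2.3 says: "Procedure cannot be commenced. No harm to participant". Section 11.2.2 lists device failure or a jammed spool with no stent placed. Section 11.2.1 lists a ureteric orifice that cannot be seen. Section 5.1 sends a participant with no stent after the first attempt to the operating room.

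**The concern.** The endpoint asks whether the device can place a stent correctly. Attempts in which it cannot start or cannot deploy are therefore among the failures it must count, yet they are the ones the written rules do not secure. There are three gaps.

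- **Denominator.** A participant who consented but whose device never started may be judged not treated and fall out of a set that is labelled intent-to-treat.
- **Scoring.** A participant in whom the device was used without placing a stent has nothing to show on a post-insertion X-ray. No rule turns that into a No, and the bar on imputation invites leaving it blank. A persistent Unsure has a clinical consequence but no stated score.
- **Reference.** Section 14.3 does not point back to the full 8.3.1 measure, so the place of an ultrasound-confirmed stent in the analysis is not stated.

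This is the only primary endpoint. The synopsis says a positive outcome leads to a pivotal trial, and section 15.8 has the safety committee review efficacy after the first five participants before more are enrolled. With so few participants, the handling of one case shows in the result.

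**Working it through.** **1. Figures in the plan.** Section 14.1 gives no power, threshold or calculated sample size, so there is none to reproduce. It prescribes exact 97% intervals for categorical variables (95% for means), so both levels are shown below.

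**2. Foreseen outcomes traced through the rules.**

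| Outcome | In the set under 14.5? | JSI stent to image? | Score stated? |
|---|---|---|---|
| Device cannot start (11.2.3) | Literally no; treated is undefined | No | No |
| Device used, no stent placed (5.1, 11.2.1, 11.2.2) | Most naturally yes | No | No |
| Stent placed, still Unsure after ultrasound (8.3.1) | Yes | Yes | Theatre, but no score |
| Stent misplaced and X-rayed | Yes | Yes | No on the 8.3.1 scale |

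The gap lies in the first three rows. The fourth is handled.

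**3. Effect on the estimate.** Inputs: N up to 15 (synopsis), and five at the first safety review (15.8). Assumption: the failures are of the no-stent type and are dropped. The interval is Clopper-Pearson, with lower limit the α/2 quantile of Beta(x, n−x+1) and upper limit the 1−α/2 quantile of Beta(x+1, n−x). When x = n the lower limit is (α/2)^(1/n); for 13/13 that is 0.025^(1/13) = 0.753 at 95% and 0.015^(1/13) = 0.724 at 97%.

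| Attempts, failures | Failures counted: rate; 95% CI; 97% CI | Failures dropped: rate; 95% CI; 97% CI |
|---|---|---|
| 15, 1 | 14/15 = 93.3%; 68.1–99.8; 65.3–99.9 | 14/14 = 100%; 76.8–100; 74.1–100 |
| 15, 2 | 13/15 = 86.7%; 59.5–98.3; 56.8–98.7 | 13/13 = 100%; 75.3–100; 72.4–100 |
| 10, 1 | 9/10 = 90.0%; 55.5–99.7; 52.1–99.8 | 9/9 = 100%; 66.4–100; 62.7–100 |
| 5, 1 | 4/5 = 80.0%; 28.4–99.5; 24.7–99.7 | 4/4 = 100%; 39.8–100; 35.0–100 |

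**4. How often a failure would arise.** Section 10.4 expects 5 to 10% of insertions to fail and go to theatre. The chance of at least one failure is 1 − (1 − f)^N. For N = 15 this is 1 − 0.95^15 = 53.7% to 1 − 0.90^15 = 79.4%, with 15 × 0.05 = 0.75 to 15 × 0.10 = 1.5 failures expected. The chance of two or more is 17.1% to 45.1%. These figures cover failures of every kind, and the protocol does not split them into no-stent and misplaced.

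For the no-connection route alone, section 11.2.3 rates the probability as Possible, which Appendix A sets at 1%. Over 15 participants that gives 1 − 0.99^15 = 14.0%.

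**The case against.** The strongest reply is that a sensible analyst would do the right thing anyway. Section 14.2 describes the treatment as the inserter itself, so a participant in whom the spool jams or the orifice is not found has been treated and stays in the set. If no stent goes in, the outcome is known and is not a success; it is not missing data, so 14.8 does not reach it. Section 5.1 says the outcome of every JSI will be recorded, and section 10.4 already calls a trip to theatre a failure. Detailed scoring can sit in the SAP, which 14.6 mentions and which is not at hand. The study is also descriptive, with no test or success threshold.

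Much of this stands. It limits the clear route out of the denominator to devices that fail before use, and it lowers the severity. It does not close the point. The intent-to-treat label conflicts with its own definition in this document. Nothing ties the record in 5.1 or the consent wording in 10.4 to the analysis set or the score. The no-imputation rule has no exception for a failed attempt.

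A reader might also infer that a stent that U-turns or is set too short would count as a success under 14.3, since it lies in the ureter. The protocol does not support that. Section 14.3 requires correct placement, and the hazard rows in 11.2.1 and 11.2.2 treat such stents as incorrectly placed. What remains against 14.3 is only the omitted collecting-system criterion and ultrasound step.

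**Conclusion.** The point holds as a defect of definition that should be fixed; it does not invalidate the study. Followed literally, sections 14.5, 8.3.1 and 14.8 allow an attempt that never starts to leave the denominator. They also leave a no-stent attempt or a persistent Unsure without a score. The reported success rate can therefore be too high.

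The size is illustrative. Under the no-stent assumption, one dropped failure in 15 moves the rate from 93.3% to 100%, and two move it from 86.7% to 100%; two is above the 0.75 to 1.5 failures the protocol expects. At the first safety review, one dropped failure turns 80% into 100%. If every failure is a misplaced stent that is X-rayed, there is no distortion.

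A reader might infer that the rate is certain to be biased upward, or that most failed insertions disappear from the analysis. The document supports neither: the mix of failure types is unknown, and participants in whom the device was used would most naturally remain in the set.

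**What to change.** - **Section 14.5.** Drop the intent-to-treat label. Define the primary set as every enrolled participant for whom a JSI package is opened for use, with no later removal. Section 13.5.2 already starts the recorded set-up time at that act, so no new data are needed. List enrolled but not attempted participants separately.
- **Section 14.3.** Refer to the 8.3.1 measure. Success is Yes on KUB, or Unsure on KUB and confirmed by the ultrasound already planned. Every other outcome is a failure: No, still Unsure, no stent deployed, device could not start, or no imaging.
- **Section 14.8.** State that this scoring is part of the endpoint definition and is not imputation.

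Opening the package is one reasonable anchor among several; what matters is that it is fixed before outcomes are known. The change is to wording only and leaves patient care as it is. Its cost is that the reported success rate may be less favourable.

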14.6 Statistical Deviations

Any post-hoc, or unplanned, analyses not identified in this CIP or in the SAP will be clearly identified in the clinical investigation report.

14.7 Interim Analysis

No interim analyses are planned for this clinical investigation.

14.8 Missing Data

Every effort will be made to collect all data points in the study. The Sponsor plans to minimise the amount of missing data by appropriate management of the prospective clinical study, proper screening of study participants, and training of participating investigators, monitors and study coordinators. All partial data that is available on participants who drop out during the course of the study will be included. No imputation will be performed for study outcomes.

15 SAFETY MONITORING AND REPORTING

15.1 Definitions

15.1.1 Adverse event (AE)

An adverse event is any untoward medical occurrence in a clinical trial participant undergoing a medical procedure that does not necessarily have a causal relationship with this treatment. These will not necessarily constitute an adverse event unless they are considered to be of concern or related to the study or the intervention in the investigator's clinical judgement. In all cases, the condition or disease underlying the symptom, sign or laboratory value should be reported.

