| 
Use of JiffyStent Inserter or insertion of stent causes pain or discomfort
 
Probability: Almost Certain Severity: Serious
 | 
Participant discomfort or pain in urethra or bladder due to insertion of JSI into the bladder without general anaesthetic.
 
Patient discomfort or pain in flank or abdomen due to the insertion of the stent up the ureter.
 | 
Readily available local anaesthetic gel and lubricating jelly inserted into the urethra prior to insertion of the device.
 
Further analgesia may include Pentrox green whistle device, oral medications, or intravenous medications such as midazolam, fentanyl, or ketamine.
 |
| 
Participant infection
 
Probability: Possible Severity: Serious
 | 
Patient develops a urinary tract infection related to the use of the device.
 
This risk should be no greater than the usual risks of infection with the standard procedure in the operating room.
 | 
Standard sterile preparation and drape as per usual set up prior to insertion of a urinary catheter.
 
Single dose of oral or intravenous antibiotics could be given at the time of the device use and stent insertion.
 |
| 
Patient experiences blood in urine.
 
Probability: Likely Severity: Serious
 | 
Patient may experience blood in urine following use of device and insertion of stent. This is usually mild and self-limiting. In very rare instances it can be very heavy bleeding with clots that may require admission to hospital and further operations. This risk should be no greater with use of the device compared to standard procedure in an operating room.
 | 
Appropriately qualified doctor performing the procedure.
 
Fully informed consent regarding possibility of blood in urine after procedure. Good instructions to participant about staying well hydrated following the procedure and represent to the hospital or contact their doctor if heavy bleeding persists.
 |
| 
Stent migration
 
Probability: unlikely Severity: Serious
 | 
The stent may migrate after initial correct positioning. This risk is unchanged from the standard procedure when inserted in an operating room.
 | 
Routine post stent insertion follow-up includes proceeding to definitive management of the stone or possibly a repeat CT of the ureter to see if the stone has passed spontaneously.
 |

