15.2 Non-reportable adverse events

There are no non-reportable adverse events.

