15.5 Reporting Requirements

15.5.1 Reporting (Serious) Adverse Events

Adverse event reporting will start at the time of signing consent. Underlying diseases are not reported as adverse events, but any deterioration in severity will be reported.

Adverse event information will be collected for all participants. At every participant visit, the investigator will determine whether an adverse event has occurred since the last visit. All adverse events will be reported in the CRF. The date of the initial event and the subsequent treatment will be documented.

The Investigator will be required to report any and all Serious Adverse Events (SAEs) that occur throughout the course of the study, regardless of causality or expectedness, to the Sponsor or designee within 24 hours of knowledge of the event.

Minimum information on the case report form will include:

- Participant initials and study number
- Nature of the event
- Commencement and cessation of the event
- An investigator's opinion of the relationship between study involvement and the event (unrelated, possibly, probably or definitively related).
- Whether treatment was required for the event and what treatment was administered.

The Sponsor is responsible to assess whether the SAE meets requirements for expedited reporting.

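### Section 15.1.1 defines an adverse event without any causal link, then lets the investigator withhold that status from occurrences judged unrelated and not of concern

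*Protocol*

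**What the plan says.** Section 15.1.1 opens broadly, without asking for a link to the treatment: "An adverse event is any untoward medical occurrence in a clinical trial participant undergoing a medical procedure that does not necessarily have a causal relationship". Its second sentence narrows this: "These will not necessarily constitute an adverse event unless they are considered to be of concern or related to the study or the intervention", to be decided "in the investigator's clinical judgement". The protocol gives no criterion for what is of concern. The section closes: "In all cases, the condition or disease underlying the symptom, sign or laboratory value should be reported".

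Later sections read as if capture were complete. Section 15.2 states "There are no non-reportable adverse events". Section 15.5.1 states "All adverse events will be reported in the CRF", starts reporting at consent, and asks for all serious adverse events (SAEs) "regardless of causality or expectedness". It also says that underlying diseases are not AEs but that their deterioration is reported. Section 15.1.3 defines an SAE as an AE that meets a seriousness criterion. Section 15.3 grades causality, with unrelated as one of four levels.

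The safety endpoint in section 8.3.2 is measured by reported AEs, device deficiencies and a participant questionnaire. The trial is single arm, without a control (section 14.2), in up to 15 participants.

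**The concern.** The second sentence of 15.1.1 makes AE status depend on a judgement of relatedness or importance, which the first sentence rules out as a requirement. That judgement belongs after recording, under 15.3 and 15.4, where the sponsor assesses it as well and where a doubtful case defaults to possibly related. Placed in the definition, it is made by the investigator alone and leaves no record.

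This matters because safety is in the title and aim of a first-in-human study. Group 2 presents with renal colic, which section 5.2 describes as flank pain with nausea, vomiting and sometimes visible haematuria. Section 11.2.1 lists flank pain and blood in the urine as risks of the device and stent too. The same symptom can be put down to the stone or to the procedure, and there is no control group to separate the two. Section 9.12 itself names the investigator's misjudgement of how SAEs relate to the device as a potential confounder. The safety committee decides on further enrolment after the first five participants (section 15.8) and sees only what was recorded.

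**Working it through.** The protocol states no figure on this point, so there is none to reproduce. The check is a reading of the sections in order, followed by an illustration of scale.

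**1. What the filter can remove.** The test is of concern *or* related. Failing it requires failing both limbs:

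| Investigator's judgement | Of concern | Not of concern |
|---|---|---|
| Related | AE | AE |
| Unrelated | AE | need not be an AE |

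Only the last cell is exposed.

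**2. Whether a later section restores it.**
- 15.2 and the CRF rule in 15.5.1 speak of AEs, so an occurrence that was denied AE status is outside them.
- 15.3 grades events already recorded. Its unrelated level can receive events that are unrelated but of concern, not those in the exposed cell. Its default to possibly related likewise applies only to a recorded event.
- 15.1.3 makes SAEs a subset of AEs, so the filter formally precedes the rule to report SAEs whatever their cause.
- The closing sentence of 15.1.1 preserves the underlying condition, not the occurrence. Where that condition is the known stone, 15.5.1 says that underlying disease is not an AE unless it deteriorates.

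Nothing downstream brings the exposed cell back.

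**3. Direction.** The sentence can only subtract. Recorded AE counts are lower or unchanged, never higher.

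**4. Scale.** Exact (Clopper–Pearson) intervals with n = 15 at the 97% level that section 14.1 prints for categorical variables. For zero events the upper limit is 1 − 0.015^(1/15) = 24.4%.

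| Participants with a recorded event | Proportion | Exact 97% CI |
|---|---|---|
| 2/15 | 13.3% | 1.3%–43.2% |
| 1/15 | 6.7% | 0.1%–34.7% |
| 0/15 | 0% | 0%–24.4% |

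One lost event moves the result down one row.

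**5. Chance of recording at least one event.** Let p be the true risk per participant and q the share filtered out. The chance is 1 − (1 − p(1 − q))^15. The documents give neither p nor q; the values below are assumptions for illustration.

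| Assumed p | q = 0 | q = 25% | q = 50% |
|---|---|---|---|
| 10% | 0.794 | 0.689 | 0.537 |
| 20% | 0.965 | 0.913 | 0.794 |

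For example, p = 10% and q = 50% give 1 − 0.95^15 = 0.537.

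**The case against.** A reader might infer that the AE rate could be reported anywhere from 15/15 to 0/15 in the same participants, because section 11.2.1 rates procedural pain "Probability: Almost Certain Severity: Serious" and haematuria as likely. The documents do not support this. Section 11.2.1 ties both to use of the device or insertion of the stent, so they are related and remain AEs even if thought unimportant. Their severity rating means, in Appendix A, that professional medical intervention is needed, which is hard to square with being of no concern. Nor does 15/15 follow: the urethral and bladder pain listed there is from insertion without general anaesthetic, and the five Group 1 participants have one.

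A reader might also see a literal contradiction with section 15.2. Strictly, 15.2 covers what is already an AE, and the filter acts one step earlier. That clash is one of effect; the literal contradiction lies inside 15.1.1.

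The strongest point in the plan's favour is that the second sentence opens with a pronoun that has no clear antecedent, while the closing sentence speaks of a symptom, sign or laboratory value. The filter was probably meant for isolated findings. That is a fair guess at intent, but the printed text does not say so, and sites follow the printed text.

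There are also real safeguards. Device deficiencies and the questionnaire are unfiltered parts of the safety endpoint. Section 13.5 collects pain before, during and after treatment, difficulties, complications and tolerance. Section 15.5.1 asks for deterioration of underlying disease. Source data are verified (section 9.13). These reduce the loss, but they do not replace AE counts graded for severity and causality.

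**Conclusion.** The point holds as an internal contradiction in 15.1.1 with a one-sided consequence. Followed as written, the section allows occurrences judged both unrelated and not of concern to go unrecorded, ungraded and unseen by the sponsor and the safety committee. The likeliest candidates are symptoms in Group 2 attributed to the stone, and events judged minor. Events judged device-related are not at risk.

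The bias is possible rather than certain, since the sentence permits exclusion without requiring it. Its direction is downward. Its size cannot be derived from the documents; the probabilities above rest on assumed risks and filtering shares. At this sample size a single event matters: its loss can turn 1/15 into 0/15. The point is not one for the statistical analysis plan, because an event that was never recorded cannot be recovered at analysis.

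**What to change.** Delete the second sentence of 15.1.1. Alternatively, limit it expressly to isolated signs, symptoms or laboratory values without clinical consequence, which is what the closing sentence of the section seems to intend.

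State that every untoward occurrence from consent to the last visit is entered on the AE form, and only then graded for severity (15.4) and causality (15.3). Keep the rule in 15.5.1 that underlying disease counts only when it deteriorates, and refer to it in 15.1.1, so that presenting colic is treated the same way throughout. Align 15.1.1 with 15.2 and 15.5.1.

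Tabulate all AEs, and separately those related to the device or procedure.

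The cost is one sentence in the protocol and a few more AE forms for at most 15 participants. The change should be made before the first participant consents, as it governs what the site writes down.
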